9.2.6. JAKi Reporting Periods

For analyses evaluating changes in the use of tofacitinib according to updated recommendations in the JAKi 2022/2023 Article 20 referral, the indexing period will be split into the following 3 periods:

- **Reporting period 1**: which will cover the 63-month period after the initial distribution of the aRMM materials but prior to the PRAC/CHMP's notification of the JAKi referral (01 January 2018 through 31 March 2023, to allow for dissemination of DHPC letters);
- Reporting Period 2, which will cover the 5-month period after the PRAC/CHMP's notification of the JAKi referral, through initial distribution and uptake of the JAKi referral aRMM materials (01 April 2023 through 31 August 2023); and
- **Reporting Period 3**, which will cover the 16-month period after the period of initial distribution and uptake of the JAKi referral aRMM materials (01 September 2023 through 31 December 2024).

See Figure 5 for an overview of the JAKi Reporting Periods 1-3.

Figure 5. Overview of the JAKi Reporting Periods

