9.2.4. Venous Thromboembolism Reporting Periods

For analyses evaluating changes in the use of tofacitinib in patients with VTE risk factors, the indexing period will be split into the following 3 periods:

- **Reporting Period 1**, which will cover the 17-month period after the initial distribution of the aRMM materials but *prior to* the PRAC/CHMP's notification of an increased risk of VTE among patients already at high risk (01 January 2018 through 31 May 2019, to allow for dissemination of DHPC letters following announcement of the provisional measures);
- Reporting Period 2, which will cover the 17-month period after the PRAC/CHMP's notification of an increased risk of VTE and mortality, through initial distribution and uptake of the 2019 Article 20 referral aRMM materials (01 June 2019 through 31 October 2020); and
- **Reporting Period 3**, which will cover the 50-month period after the period of initial distribution and uptake of the 2019 Article 20 referral aRMM materials (01 November 2020 through 31 December 2024).

See Figure 3 for an overview of the VTE Reporting Periods 1-3.

Figure 3. Overview of the Venous Thromboembolism Reporting Periods

^{*}Aligned with the first reimbursed prescription record in SNDS

[figure not shown]

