9.2.5. Cardiovascular and Malignancy Reporting Periods

For analyses evaluating changes in the use of tofacitinib in patients with CV risk factors and patients with malignancy risk factors, the indexing period will be split into the following 3 periods:

- **Reporting Period 1**, which will cover the 42-month period after the initial distribution of the aRMM materials but *prior to* the PRAC/CHMP's notification of an increased risk of CV-related outcomes and malignancy-related outcomes among patients already at high risk (01 January 2018 through 30 June 2021, to allow for dissemination of DHPC letters);
- Reporting Period 2, which will cover the 16-month period of and after the PRAC/CHMP's notification of restrictions on use in the context of increased risk of CV-related outcomes and malignancy-related outcomes, through initial distribution and uptake of the 2021 signal evaluation procedure aRMM materials (01 July 2021 through 31 October 2022); and
- **Reporting Period 3**, which will cover the 26-month period *after* the period of initial distribution and uptake of the 2021 signal evaluation procedure aRMM materials (01 November 2022 through 31 December 2024).

See Figure 4 for an overview of the CV and Malignancy Reporting Periods 1-3.

Figure 4. Overview of the Cardiovascular and Malignancy Reporting Periods

^{*}Aligned with the first reimbursed prescription record in the French database

[figure not shown]

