9.7.2.4.4. Patients with malignancy risk factors

To describe changes in the utilisation of tofacitinib, this analysis will be stratified by the CV and malignancy reporting periods 1, 2 and 3. The proportion of patients with one or more malignancy risk factors, identified prior to tofacitinib initiation, will be described and tabulated overall and for each individual malignancy risk factor.

Logistic regression analyses will be used to calculate odds ratios along with their corresponding 95% confidence intervals and p values to formally compare the proportion of patients with malignancy risk factors across CV and malignancy reporting period 1, 2 and 3.

To enhance statistical power in detecting changes, a composite score for the malignancy risk factors will also be generated by summing the individual malignancy risk factors. Linear regression analyses will be employed to compare the malignancy composite score across the CV and malignancy reporting periods. In addition to the summed composite score, the same analysis using a composite score weighting the risk factors may be performed in an exploratory fashion (weights will be developed and described in the SAP). Regression coefficients with their 95% confidence intervals and p values will be generated.

Proportions may be stratified by age (≥65 years versus < 65 years) and prior use of alternative therapy (e.g., biologic), pending sufficient sample size.

The proportion of patients who discontinue or continue to facitinib after developing one or more malignancy risk factors while taking to facitinib will be described separately. Proportions will be stratified by age (≥65 years versus < 65 years) and prior use of alternative therapy (e.g., biologic), pending sufficient sample size.

9.7.2.5. Describe prescribing patterns over time: Describe changes in the utilisation of tofacitinib following the updated recommendations and limitations for use implemented after the JAKi 2022/2023 Article 20 referral

9.7.2.5.1. UC maintenance treatment dosage for patients with CV and malignancy risks, in addition to VTE risk factors

To describe changes in the utilisation of tofacitinib, this analysis will be stratified by the JAKi reporting periods 1, 2 and 3. The proportion of UC patients with CV or malignancy risk factors who have an ADD of > 10 mg in Weeks 17-24, Weeks 25-32, Weeks 33-40 and/or Weeks 41-48 of follow-up will be described and tabulated over each of the JAKi reporting periods.

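### Each set of reporting periods is cut around one measure only, so the Period 3 versus Period 1 contrasts cannot separate that measure from the other two; follow-up outcomes are also filed by start date.

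*Protocol*

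**What the plan says.** All three schemes divide patients by index date. Section 9.2.6 states that "the indexing period will be split into the following 3 periods", and Sections 9.2.4 and 9.2.5 do the same.

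- **VTE set (9.2.4).** Period 1 runs from January 2018 to May 2019 and Period 2 from June 2019 to October 2020. Period 3 is the one "which will cover the 50-month period after the period of initial distribution and uptake of the 2019 Article 20 referral aRMM materials", November 2020 to December 2024.
- **CV/malignancy set (9.2.5).** Period 1 is "01 January 2018 through 30 June 2021, to allow for dissemination of DHPC letters". Period 2 runs from the notification "through initial distribution and uptake of the 2021 signal evaluation procedure aRMM materials (01 July 2021 through 31 October 2022"). Period 3 is "01 November 2022 through 31 December 2024".
- **JAKi set (9.2.6).** Period 1 is the one "which will cover the 63-month period after the initial distribution of the aRMM materials but prior to" the JAKi notification, January 2018 to March 2023. Period 2 is April to August 2023. Period 3 is the one "which will cover the 16-month period after the period of initial distribution and uptake of the JAKi referral aRMM materials", September 2023 to December 2024.

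Section 9.5 makes Period 3 versus Period 1 the primary comparison and treats Period 1 as the baseline before the updated materials. For the UC maintenance dose in Weeks 17–48, Section 9.7.2.5.1 says that "this analysis will be stratified by the JAKi reporting periods 1, 2 and 3". Section 9.7 tests whether reductions are statistically significant. Section 7 says the results, with those of two other studies, will be used to judge whether the materials are effective.

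**The concern.** Two separate problems follow from these cuts.

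**Overlap of measures.** A Period 1 that already contains an earlier measure is not a clean baseline, and a Period 3 that contains a later measure is not a clean after-period. This would matter less if the three sets looked at different patients. They do not. In Table 3, age ≥65, diabetes and hypertension count as both VTE and CV factors, and age ≥65 and malignancy count as both VTE and malignancy factors. Section 7 records that the 2019 referral already addressed the UC maintenance dose in patients with VTE risk factors, which is the subject the JAKi update later extended. The regressions in Sections 9.7.2.4 and 9.7.2.5 state no term for the other measures. The comment in the ENCePP checklist (Annex 2, Section 7) says confounding is not a concern, and Section 9.9 does not mention the overlap.

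**Index-date filing.** Risk factors, age and prior biologic use are fixed at initiation. The dose in Weeks 17–48, discontinuation, continuation and turning 65 occur later, and may fall after a notification although the patient is filed before it.

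At stake is which set of materials is said to have worked.

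**Working it through.** **1. The plan's own figures.** Counting months from the stated dates gives 17/17/50, 42/16/26 and 63/5/16, as printed. The formula in Section 9.5, n = (1.96 + 0.84)² [p₁(1−p₁) + p₂(1−p₂)] / d², reproduces all nine rows of Table 5 (for example 70% versus 60% gives 354). The lengths and sample sizes are correct. The difficulty lies in where the periods sit.

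**2. Overlap in months**, taking each measure to start at its own Period 2 (1 June 2019, 1 July 2021, 1 April 2023):

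| Period | Other measure | Months after it |
|---|---|---|
| VTE Period 3 | 2021 signal | 42 of 50 (84%) |
| CV/malignancy Period 1 | VTE | 25 of 42 (60%) |
| CV/malignancy Period 3 | JAKi | 21 of 26 (81%) |
| JAKi Period 1 | VTE | 46 of 63 (73%) |
| JAKi Period 1 | 2021 signal | 21 of 63 (33%) |

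**3. How large a borrowed contrast could be.** Section 9.5 projects 4,000 RA/PsA and 1,000 UC patients to December 2020, and 8,000 and 2,000 to December 2024. Assumptions not in the protocol: even accrual within 2018–2020 and within 2021–2024, UC counted from May 2019 (Section 9.2.2), and a 10-point step caused by one *other* measure only. Monthly accrual is then 111.1 and later 83.3 for RA/PsA, and 50 and later 20.8 for UC.

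- *VTE contrast, only the 2021 signal acts.* Period 3 holds 2 × 111.1 + 48 × 83.3 = 4,222 RA/PsA patients. With the step at July 2021, 3,500 follow it, so the contrast shows 10 × 3,500/4,222 = 8.3 points. With the step at November 2022 it shows 10 × 2,167/4,222 = 5.1 points. Chance of p<0.05: 96–100% over baselines of 30–80%.
- *CV/malignancy contrast, only the VTE measure acts.* Period 1 holds 4,500 RA/PsA patients. Those indexed before the step number 3,778 (step November 2020) or 1,889 (step June 2019), giving 8.4 or 4.2 points. Chance of p<0.05: 90–100%.
- *UC JAKi contrast, no JAKi effect.* Period 1 holds 20 × 50 + 27 × 20.8 = 1,562 patients. A VTE step at November 2020 gives 10 × 900/1,562 = 5.8 points. A 2021-signal step at November 2022 gives 10 × 1,458/1,562 = 9.3 points. Chance of p<0.05: 48–95% if all UC patients count. This is an upper bound, because the outcome concerns those with CV or malignancy risk factors.

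**4. Index-date filing of the JAKi dose outcome.** Weeks 17–48 run from index + 112 to index + 335 days.

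- Index 30 April 2022 + 335 = 31 March 2023, so patients indexed from 1 May 2022 have some of the window after the notification.
- Index 10 December 2022 + 112 = 1 April 2023, so patients indexed from then have all of it after.
- At the projected accrual these are about 230 (15%) and 77 (5%) of JAKi Period 1 UC patients, and about 10% of that period's maintenance time is post-notification.
- For JAKi Period 2 starters, with even index dates, 2.5% of maintenance days fall in Period 2 and 97.5% in calendar Period 3.

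**5. Narrow windows or step terms for UC?** Limiting the JAKi comparator to November 2022–March 2023 leaves 5 × 20.8 = 104 UC patients against 333 in Period 3. That is below the 160–354 of Section 9.5, with power of roughly 44–56% for 10 points. With step terms at the three notification cuts, the JAKi step instead compares July 2021–March 2023 with April 2023 onwards: 21 × 20.8 = 437 patients on each side.

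**The case against.** Several points on the other side are sound.

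- *The primary comparison is not misfiled.* Section 9.5 defines it on risk factors among initiators, fixed at index. A reader might infer that index-date filing invalidates it; the document does not support that. The filing problem is confined to follow-up outcomes, and of these Sections 9.7.2.4.2 and 9.7.2.5.1 plan formal tests only for turning 65 and the JAKi dose. The other follow-up outcomes are only described.
- *The 97.5% figure concerns JAKi Period 2*, which enters secondary comparisons only. For Period 3 versus Period 1 the effect is about 10% contamination, which pulls the contrast toward no change.
- *The measures are partly separated already.* VTE Period 2 ends before the 2021 signal and CV/malignancy Period 2 before the JAKi notification, and Section 9.5 plans Period 1 versus Period 2. Table 3 has a VTE outcome restricted to factors other than CV or malignancy factors. Age-65 outcomes are shown by both sets of periods.
- *The stated aim is to describe and contextualise*, and effectiveness is judged together with two other studies.

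These safeguards help only in part. CV/malignancy Period 1 versus 2 keeps a baseline with 25 of 42 months after the VTE notification. The restricted VTE outcome is still touched by the JAKi update, which by Section 7 includes advice on exactly those factors; 21 of the 50 months of VTE Period 3 follow 1 April 2023. The descriptive aim sits beside significance tests and a planned use in judging effectiveness. The periods and the primary contrast are fixed in the protocol, not left to the SAP.

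**Conclusion.** The point holds in this form: the Period 3 versus Period 1 contrasts cannot tell the measures apart, so a change may be partly or wholly due to another measure. It would go too far to say that the contrasts *do* credit the wrong measure. The document shows that this can happen, not that it will.

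The overlap is the larger problem: 33% to 84% of the affected periods follow another measure's cut. That rests on the protocol's dates alone. The borrowed contrasts of 4 to 9 points rest on an assumed 10-point step and even accrual, and illustrate rather than predict.

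Misfiling of follow-up outcomes is smaller and separate. For the UC JAKi dose it affects about 15% of Period 1 patients in part and 5% wholly, and dilutes the primary contrast. The change is advisable and needs no new data.

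**What to change.** 1. Keep the index-date cut for initiation outcomes. For each outcome set add one regression on the common calendar axis with step terms at all three measures, and base measure-specific statements on it. Do not rely on narrow bounded windows, which leave too few UC patients. In UC the VTE notification step would rest on one month of earlier data (May 2019, about 50 patients), and this should be said.
2. For the patient-level JAKi dose outcome, define *before* as Weeks 17–48 ending before 1 April 2023 (index to 30 April 2022). Define *after* as Weeks 17–48 starting on or after 1 September 2023 (index from 12 May 2023, since 12 May + 112 days = 1 September). Treat those between as transition. At the projected accrual this gives about 1,000 + 16 × 20.8 = 1,333 UC patients before, 19.65 × 20.8 = 409 after and 257 in transition. The before group still spans the two earlier measures, so it needs the step terms as well.
3. Date turning-65, discontinuation and continuation outcomes by the calendar date of the event.
4. Keep the present cut as secondary, and state in Section 9.9 that it does not isolate single measures.

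Cost: protocol and SAP wording, recoding of the period variable, some extra modelling, and wider intervals, especially for UC.

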9.3. Variables

9.3.1. Variables and definitions

Table 3 summarises and defines the study variables to be collected and analysed in SNDS. Unless otherwise specified, these variables will be assessed during each patient's entire study period (baseline period and follow-up period).

This study will use code-based algorithms from the literature and/or other code lists to identify study variables. Published validated algorithms will be used where available.^{6, 7} All code-based algorithms and code lists will be reviewed and/or approved by Pfizer prior to

study initiation. Preliminary algorithms and/or codes are proposed in the following (Table 3); see also Annexes). Final algorithms and/or code lists may be refined as part of the statistical analysis plan (SAP) development. It is also to be noted that while laboratory tests performed are captured, results of laboratory tests are not available in the SNDS database.

Table 3. Operational definitions of study variables in Système National des Données de Santé

Variable	Role	Operational definition
Exposure		
Tofacitinib treatment	Exposure	Defined as having ≥1 ATC code (L04AA29) for a reimbursed prescription of tofacitinib during the indexing period. Index date is defined as the date of the first reimbursed prescription of tofacitinib.
Indication		
Indication	Indication (including off-label use)	Reported in the following categories: RA, PsA, UC and off-label/unknown based on hospital discharge diagnoses and active registration for diagnoses reported in the long-term disease (LTD) database for outpatients in the relevant time period. If there are no diagnosis codes for RA, PsA or UC, it will be categorised as off-label/unknown indications. Details will be further developed in the SAP.
		List of diagnoses codes for indications in ANNEX 13. LIST OF DIAGNOSIS CODES FOR INDICATIONS.
Primary Objective 1: I	Demographics, comorbi	dities and prior and current medications
		T OF CODES FOR COMORBIDITIES, unless otherwise
Age at tofacitinib initiation	Demographic	Calculated as the date of tofacitinib initiation minus the patient's month and year of birth and reported in the following categories: <18 years, 18-29 years and 30-39 years; 40-49 years; 50-59 years; 60-69 years; 70-79 years; ≥80 years; and <65 years and ≥65 years.
Sex	Demographic	Reported in the following categories: Male, Female and Unknown. Assessed on the date of the index tofacitinib prescription dispensing.
Hepatic impairment	Comorbidity	Defined as ≥1 International Classification of Disease, 10th Revision (ICD-10) diagnosis code for hepatic impairment.
Hepatic impairment, mild or moderate	Comorbidity	Defined as ≥1 ICD-10 diagnosis code for mild or moderate hepatic impairment.
Hepatic impairment, severe	Comorbidity	Defined as ≥1 ICD-10 diagnosis code or procedure code for severe hepatic impairment.
Renal impairment	Comorbidity	Defined as ≥1 ICD-10 diagnosis code or procedure code for renal impairment
Renal impairment, mild	Comorbidity	Defined as ≥1 ICD-10 diagnosis code or procedure code for mild renal impairment
Renal impairment, moderate	Comorbidity	Defined as ≥1 ICD-10 diagnosis code or procedures code for moderate renal impairment
Renal impairment, severe	Comorbidity	Defined as ≥1 ICD-10 diagnosis code or procedure code for severe renal impairment
Herpes zoster (HZ)	Comorbidity	Defined as ≥1 ICD-10 diagnosis code for HZ.

Table 3. Operational definitions of study variables in Système National des Données de Santé

Variable	Role	Operational definition
Human immunodeficiency virus (HIV)	Comorbidity	Defined as ≥1 ICD-10 diagnosis code for HIV.
Tuberculosis (TB), including both active and latent TB	Comorbidity	Defined as ≥1 ICD-10 diagnosis code for TB.
Viral hepatitis B or C	Comorbidity	Defined as ≥1 ICD-10 diagnosis code for viral hepatitis B or C.
Serious and opportunistic infections of interest (including HIV, HZ, TB and viral hepatitis B and C)	Comorbidity	Defined as ≥1 ICD-10 diagnosis code for a serious and/or opportunistic infection of interest. Complete list in ANNEX 3. LIST OF DIAGNOSIS CODES FOR SELECT INFECTIONS OF INTEREST
Diverticulitis	Comorbidity	Defined as ≥1 ICD-10 diagnosis code for diverticulitis.
Malignancy (non- metastatic and metastatic, excluding NMSC)	Comorbidity	Defined as ≥1 ICD-10 diagnosis code for a malignancy (excluding NMSC).
NMSC	Comorbidity	Defined as ≥1 ICD-10 diagnosis code for NMSC.
Gastrointestinal perforation	Comorbidity	Defined as ≥1 ICD-10 diagnosis code for gastrointestinal perforation.
Interstitial lung disease	Comorbidity	Defined as ≥1 ICD-10 diagnosis code for interstitial lung disease. Complete list in ANNEX 6. LIST OF DIAGNOSIS AND PROCEDURE CODES FOR INTERSTITIAL LUNG DISEASE
Diabetes	Comorbidity	Defined as ≥1 ICD-10 diagnosis code for diabetes or ≥3 (or at least 2 in case of large pack sizes) prescription dispensing of oral antidiabetic agents and/or insulin (identified by ATC codes).
Immunodeficiencies of interest	Comorbidity	Defined as ≥1 ICD-10 diagnosis code for immunodeficiency. Complete list in ANNEX 5. LIST OF DIAGNOSIS CODES FOR SELECT IMMUNODEFICIENCIES OF INTEREST.
Prior use of corticosteroids	Medication history	Defined as ≥1 prescription dispensing of a corticosteroid (as identified by ATC code[s]) in the 12 months prior to the index tofacitinib dispensing. Complete list in ANNEX 4. LIST OF ATC CODES FOR COMEDICATIONS OF INTEREST
Prior use of statins	Medication history	Defined as ≥1 prescription dispensing of a statin (as identified by ATC code[s]) in the 12 months prior to the index tofacitinib dispensing. Complete list in ANNEX 4. LIST OF ATC CODES FOR COMEDICATIONS OF INTEREST.

Table 3. Operational definitions of study variables in Système National des Données de Santé

Variable	Role	Operational definition
Prior use of any biologic	Medication history	Defined as ≥1 prescription dispensing of a biologic (as identified by ATC code[s]) in the 12 months prior to the index tofacitinib dispensing. Complete list in ANNEX 7. LIST OF ATC CODES FOR MEDICATIONS OF INTEREST TO AVOID WHILE TAKING TOFACITINIB.
Prior use of conventional synthetic DMARDs (csDMARDs)/ Immunomodulators	Medication history	Defined as ≥1 prescription dispensing of a csDMARD/ Immunomodulators (as identified by ATC code[s]) in the 12 months prior to the index tofacitinib dispensing. Complete list in ANNEX 7. LIST OF ATC CODES FOR MEDICATIONS OF INTEREST TO AVOID WHILE TAKING TOFACITINIB.
Prior use of MTX	Medication history	Defined as ≥1 prescription dispensing of MTX (as identified by ATC code L04AX03) in the 12 months prior to the index tofacitinib dispensing.
Prior use of anti-TB therapy	Medication history	Defined as ≥1 prescription dispensing of anti-TB therapy (as identified by ATC code[s]) in the 12 months prior to the index tofacitinib dispensing.
Prior vaccination	Medication history	Defined as ≥1 procedure code, ≥1 ICD-10 code and/or ≥1 reimbursed prescription (as identified by ATC code[s]) for a vaccination, overall and stratified by live and non-live vaccinations (if available) in the 12 months prior to the index tofacitinib dispensing. Complete list in ANNEX 4. LIST OF ATC CODES FOR COMEDICATIONS OF INTEREST.
Concomitant use of a contraindicated potent immunosuppressants	Comedication	Defined as ≥30 overlapping days' supply of a tofacitinib prescription dispensing and a prescription dispensing for a contraindicated potent immunosuppressants (as identified by ATC code[s]) during the follow-up period. Days of supply in SNDS will be approximated by reimbursed package size and per recommended posology. Duration of tofacitinib therapy defined in Section 9.3.2.
Concomitant use of MTX	Comedication	Defined as ≥30 overlapping days' supply of a tofacitinib prescription dispensing and a prescription dispensing for MTX during the follow-up period.
Concomitant use of a corticosteroid	Comedication	Defined as ≥30 overlapping days' supply of a tofacitinib prescription dispensing and a prescription dispensing for a corticosteroid (as identified by ATC code[s]) during the follow-up period.
Concomitant use of anti-TB therapy	Comedication	Defined as ≥30 overlapping days' supply of a tofacitinib prescription dispensing and a prescription dispensing for anti-TB therapy (as identified by ATC code[s]) during the follow-up period.

Table 3. Operational definitions of study variables in Système National des Données de Santé

Variable	Role	Operational definition
Primary Objective 2: Pr	escribers' adherenc	e to the tofacitinib aRMMs
		per indication and duration of use
Duration of tofacitinib	Outcome:	Defined in Section 9.3.2. Assessed during the follow-up
therapy	Adherence to	period.
	recommended	
	posology	
ADD	Outcome:	Defined in Section 9.3.3. Assessed during the follow-up
	Adherence to	period.
	recommended	
	posology	
A patient with an	Outcome:	Among RA/PsA patients is defined as 0 ICD-10 diagnosis
ADD of >11 mg	Adherence to	code for UC during baseline or follow-up period and an
during any of the 8-	recommended	ADD of >11 mg during any of the 8-week intervals.
week intervals and no	posology	
evidence of a		
diagnosis for UC		
A patient with an	Outcome:	Among UC patients, is defined as ≥ 1 prescription dispensing
ADD of ≥15 mg in	Adherence to	for a biologic (as identified by ATC codes) prior to the index
Weeks 17-24, Weeks	recommended	tofacitinib dispensing and an ADD ≥15 mg in any of the
25-32, Weeks 33-40 or	posology	intervals: Weeks 17-24, Weeks 25-32, Weeks 33-40 or
Weeks 41-48 of		Weeks 41-48 of follow-up.
follow-up and with		Complete list of biologics in ANNEX 7. LIST OF ATC
evidence of a		CODES FOR MEDICATIONS OF INTEREST TO AVOID
diagnosis for UC but		WHILE TAKING TOFACITINIB
no use of an		Note: This definition will miss those who have one 10 mg
alternative therapy		BID prescription and the remaining prescriptions are 5 mg
(i.e., biologic) prior to		BID.
tofacitinib initiation		
A patient who has	Outcome:	Among UC patients, is defined as ≥ 1 prescription dispensing
known VTE, CV or	Adherence to	for a biologic (as identified by ATC codes) prior to the index
malignancy risk	recommended	tofacitinib dispensing and an ADD >10 mg in any of the
factors with an ADD	posology	intervals: Weeks 17-24, Weeks 25-32, Weeks 33-40 or
of >10 mg in Weeks		Weeks 41-48 of follow-up and ≥1 VTE, CV or malignancy
17-24, Weeks 25-32,		risk factors from baseline to Week 16.
Weeks 33-40 or		
Weeks 41-48 of		An ADD \geq 15 mg in the definition above will be used in a
follow-up and with		sensitivity analysis.
evidence of a		
diagnosis for UC but		
no use of an		
alternative therapy		
(i.e., biologic) prior to		
tofacitinib initiation		

Adherence to patient screening and laboratory monitoring prior to and during tofacitinib treatment

The following recommended screenings and monitoring will be assessed in the following time frames:

- In the 30 days prior to and including the day of tofacitinib initiation;
- In the 31 to 60 days prior to tofacitinib initiation;

Table 3. Operational definitions of study variables in Système National des Données de Santé

Donnees de Sante			Donnees	
	Variable	Role		Operational definition

- In the 61 to 90 days prior to tofacitinib initiation; and
- In the 91 to 180 days prior to tofacitinib initiation;

For patients with at least 6 months of tofacitinib therapy (duration of tofacitinib therapy defined in Section 9.3.2):

- In the 60 days after the day of tofacitinib initiation;
- In the 61 to 120 days after tofacitinib initiation; and
- In the 121 to 180 days after to facitini binitiation.

For patients with 12 months of tofacitinib therapy (duration of tofacitinib therapy defined in Section 9.3.2):

- In the 181 to 240 days after tofacitinib initiation;
- In the 241 to 300 days after to facitinib initiation; and
- In the 301 to 360 days after to facitinib initiation.

For analyses, 1 month will be defined as 30 days and 1 year will be defined as 360 days.

List of laboratory codes in ANNEX 10. LIST OF LABORATORY TEST CODES.

List of laboratory codes	III THI TILL TO. LIDT	OF EMBORITORY TEST CODES.
Creatinine (serum or	Outcome:	Defined as ≥1 procedure code or ≥1 ICD-10 diagnosis code
urine) laboratory	Screening	for a creatinine (serum or urine) laboratory test.
testing		
TB screening	Outcome:	Defined as ≥1 procedure code or ≥1 ICD-10 diagnosis code
•	Screening	for TB (active and latent) screening.
	Outcome:	
	Monitoring	
Viral hepatitis B and C	Outcome:	Defined as ≥1 procedure code or ≥1 ICD-10 diagnosis code
screening	Screening	for viral hepatitis B and C screening.
-	Outcome:	
	Monitoring	
Absolute lymphocyte	Outcome:	Defined as ≥1 procedure code or ≥1 ICD-10 diagnosis code
count (ALC)	Screening	for ALC laboratory testing.
laboratory testing	Outcome:	
	Monitoring	
Absolute neutrophil	Outcome:	Defined as ≥1 procedure code or ≥1 ICD-10 diagnosis code
count (ANC)	Screening	for ANC laboratory testing.
laboratory testing	Outcome:	
	Monitoring	
Haemoglobin	Outcome:	Defined as ≥1 procedure code or ≥1 ICD-10 diagnosis code
laboratory testing	Screening	for haemoglobin laboratory testing.
	Outcome:	
	Monitoring	
Alanine	Outcome:	Defined as ≥1 procedure code or ≥1 ICD-10 diagnosis code
aminotransferase	Screening	for ALT and/or AST laboratory testing.
(ALT) and/or	Outcome:	
Aspartate	Monitoring	
aminotransferase		
(AST) laboratory		
testing		

Table 3. Operational definitions of study variables in Système National des Données de Santé

Variable	Role	Operational definition
Lipid panel (i.e., total	Outcome:	Defined as ≥1 procedure code or ≥1 ICD-10 diagnosis code
cholesterol, high-	Monitoring	for lipid panel laboratory testing.
density lipoprotein		
(HDL), low-density		
lipoprotein (LDL) and		
triglycerides (TG))		
laboratory testing		
Describe prescribing p	atterns over time: De	scribe changes in the utilisation of tofacitinib following the
		or use after the 2019 Article 20 referral, the 2021 signal
evaluation procedure,	and the 2022/2023 JA	Ki Article 20 referral
Adherence to recomme	endations for limitation	ons of use in patients with VTE risk factors (will be
stratified by VTE repo	rting period 1, 2, 3)	
Assessment of VTE risk	factors prior to initiati	on of tofacitinib
Prior VTE	Outcome: changes	Defined as ≥1 ICD-10 diagnosis code for VTE in the 12
	in use in patients	months prior to the index tofacitinib dispensing.
	with VTE risk	List of VTE codes in ANNEX 12. LIST OF DIAGNOSIS
	factors	CODES FOR VTE.
History of surgery,	Outcome: changes	Defined as ≥1 procedure code for a major surgery in the
major	in use in patients	3 months prior to the index tofacitinib dispensing.
	with VTE risk	
	factors	
Prior MI	Outcome: changes	Defined as ≥1 ICD-10 diagnosis code for an MI in the 3
	in use in patients	months prior to the index tofacitinib dispensing.
	with VTE risk	
	factors	
History of heart failure	Outcome: changes	Defined as ≥1 ICD-10 diagnosis code for heart failure in the
, ,	in use in patients	12 months prior to the index tofacitinib dispensing.
	with VTE risk	
	factors	
History of combined	Outcome: changes	Defined as ≥1 reimbursed prescription of a combined
hormonal	in use in patients	hormonal contraceptives and/or hormonal replacement
contraceptives or	with VTE risk	therapy (as identified by ATC codes) in the 12 months prior
hormonal replacement	factors	to the index tofacitinib dispensing.
therapy		
History of inherited	Outcome: changes	Defined as ≥1 ICD-10 diagnosis code for inherited
coagulation disorder	in use in patients	coagulation disorder in the 12 months prior to the index
	with VTE risk	tofacitinib dispensing.
	factors	torustamo dispensing.
History of malignancy	Outcome: changes	Defined as ≥1 ICD-10 diagnosis code for malignancy
(non-metastatic and	in use in patients	(excluding NMSC) in the 12 months prior to the index
metastatic, excluding	with VTE risk	tofacitinib dispensing.
NMSC)	factors	
Age ≥65 years	Outcome: changes	Defined as age at tofacitinib initiation ≥65 years.
1150 -00 / 0410	in use in patients	2011100 as ago at totacidino initiation =00 yours.
	with VTE risk	
	factors	
	1401015	

Table 3. Operational definitions of study variables in Système National des Données de Santé

Variable	Role	Operational definition
History of diabetes	Outcome: changes in use in patients with VTE risk factors	Defined as ≥1 ICD-10 diagnosis code for diabetes or ≥3 (or at least 2 in case of large pack sizes) prescription dispensing of oral antidiabetic agents and/or insulin (identified by ATC codes) in the 12 months prior to the index tofacitinib dispensing.
History of hypertension	Outcome: changes in use in patients with VTE risk factors	Defined as ≥1 ICD-10 diagnosis code for hypertension or ≥3 (or at least 2 in case of large pack sizes) prescription dispensing of antihypertensive agents (identified by ATC codes) in the 12 months prior to the index tofacitinib dispensing. ANNEX 8. LIST OF ATC CODES FOR ANTIHYPERTENSIVES
Initiating tofacitinib with ≥1 VTE risk factor(s)	Outcome: changes in use in patients with VTE risk factors	Defined as ≥1 VTE risk factor(s) (as listed and defined above) identified in the 12 months prior to the index tofacitinib dispensing.
Initiating tofacitinib with ≥1 VTE risk factors other than CV or malignancy risk factors	Outcome: changes in use in patients with VTE risk factors	The same definition as above but only limited to VTE risk factors other than CV or malignancy risk factors.
VTE risk factor scores	Outcome: changes in use in patients with VTE risk factors	Calculated as the sum of the number of VTE risk factors (as listed and defined above) identified in the 12 months prior to the index tofacitinib dispensing. Weighting of VTE risk factors may be considered as a sensitivity analysis to reflect the potential different
Number of UC patients with: ≥1 VTE risk factor; no prior alternative therapy (i.e., biologic); and an ADD >10 mg in Weeks 17-24, Weeks 25-32, Weeks 33-40 or Weeks 41-48 of follow-up	Outcome: changes in use in patients with VTE risk factors	importance of each risk factor. Defined as an UC patient meeting all of the following criteria: ≥1 VTE risk factor(s) (as listed and defined above) 12 months prior to the index tofacitinib prescription dispensing; 0 prescription medication dispensing for a biologic (as identified by ATC codes) in the 12 months prior to the index tofacitinib prescription dispensing; and an ADD of >10 mg in any of the intervals: Weeks 17-24, Weeks 25-32, Weeks 33-40 and Weeks 41-48 of follow-up (ADD defined in Section 9.3.3). Complete list of biologics in ANNEX 7. LIST OF ATC CODES FOR MEDICATIONS OF INTEREST TO AVOID WHILE TAKING TOFACITINIB.
Assessment of VTE risk; Section 9.3.2)	factors while receiving	tofacitinib therapy (duration of tofacitinib therapy defined in
VTE	Outcome: changes in use in patients with VTE risk factors	Defined as ≥1 ICD-10 diagnosis code for VTE while receiving tofacitinib therapy. List of VTE codes in ANNEX 12. LIST OF DIAGNOSIS CODES FOR VTE

Table 3. Operational definitions of study variables in Système National des Données de Santé

Variable	Role	Operational definition
Surgery, major	Outcome: changes in use in patients with VTE risk factors	Defined as ≥1 procedure code for a major surgery while receiving tofacitinib therapy.
MI	Outcome: changes in use in patients with VTE risk factors	Defined as ≥1 ICD-10 diagnosis code for an MI while receiving tofacitinib therapy.
Heart failure	Outcome: changes in use in patients with VTE risk factors	Defined as ≥1 ICD-10 diagnosis code for heart failure while receiving tofacitinib therapy.
Use of combined hormonal contraceptives or hormonal replacement therapy	Outcome: changes in use in patients with VTE risk factors	Defined as ≥1 prescription dispensing of a combined hormonal contraceptives and/or hormonal replacement therapy (as identified by ATC codes) while receiving tofacitinib therapy.
Inherited coagulation disorder	Outcome: changes in use in patients with VTE risk factors	Defined as ≥1 ICD-10 diagnosis code for inherited coagulation disorder while receiving tofacitinib therapy.
Malignancy (non- metastatic and metastatic, excluding NMSC)	Outcome: changes in use in patients with VTE risk factors	Defined as ≥1 ICD-10 diagnosis code for malignancy (excluding NMSC) while receiving tofacitinib therapy.
Age ≥ 65 years	Outcome: changes in use in patients with VTE risk factors	Defined as age ≥65 years while receiving to facitinib.
Diabetes	Outcome: changes in use in patients with VTE risk factors	Defined as ≥1 ICD-10 diagnosis code for diabetes or ≥3 (or at least 2 in case of large pack sizes) prescription dispensing of oral antidiabetic agents and/or insulin (identified by ATC codes) while receiving tofacitinib therapy.
Hypertension	Outcome: changes in use in patients with VTE risk factors	Defined as ≥1 ICD-10 diagnosis code for hypertension or ≥3 (or at least 2 in case of large pack sizes) prescription dispensing of antihypertensive agents (identified by ATC codes) while receiving tofacitinib therapy.
Discontinuation of tofacitinib after developing ≥1 VTE risk factors while taking tofacitinib	Outcome: changes in use in patients with VTE risk factors	Defined as ≥1 VTE risk factor(s) while receiving tofacitinib therapy (as listed and defined above) plus 0 prescription dispensing for tofacitinib within a specific time window after the code for the first VTE risk factor.
g		Note: The time window for when to look for a tofacitinib prescription dispensing will be specific to the VTE risk factor(s) acquired while receiving tofacitinib therapy and will be operationalised during SAP development.
		Duration of tofacitinib therapy defined in Section 9.3.2.

Table 3. Operational definitions of study variables in Système National des Données de Santé

Variable Role Operational definition	
Discontinuation of Outcome: changes The same definition as above but of	only limited to VTE risk
